## **SECONDARY OUTCOMES**

Secondary outcomes include antibiotic initiation by the initial ED clinician (reached if the patient received antibiotic during ED visit), hospital length of stay (number of days from ED admission to hospital discharge), 90-day and 1-year mortality (determined through a National Death Index [NDI] search or by direct contact with the patient or their listed contacts), ICU admission and subsequent ED visits by Day 30, and quality of life using AQ-20.

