Primary safety outcome(s):	Combined endpoint of adverse outcomes that could be attributable to withholding antibiotics in LRTI, by Day 30
Key secondary outcome(s):	Rate of antibiotic initiation by the initial ED clinician
Protocol Version:	Version 1.4; March 8, 2017
Source(s) of monetary or material support:	NIGMS, BioMerieux
Purpose:	To test the effect of implementation of a novel procalcitonin guideline on antibiotic and adverse outcomes in ED patients with LRTI

ProACT Coordinating Center Team

Investigators

[name], MPH
PI
Associate Professor
CRISMA Center
Departments of Critical Care Medicine, Emergency Medicine, and Clinical and Translational Science
University of Pittsburgh

[name], MPH, FRCP
Co-I
Chair, Department of Critical Care Medicine
Professor of Critical Care Medicine, Medicine, Health Policy and Management, and Clinical And Translational Science
Director, CRISMA Center
University of Pittsburgh

[name]
Co-I
Chair, Department of Emergency Medicine
Professor of Emergency Medicine
University of Pittsburgh

[name]
Co-I
Assistant Professor, Department of Medicine/Infectious Diseases
University of Pittsburgh

Investigators

[name]
Co-I
Professor, Department of Medicine
University of Pittsburgh

[name]
Co-I
Professor of Critical Care Medicine, Medicine, Bioengineering and Clinical & Translational Science
Director, Center for Critical Care Nephrology
Vice Chair for Research
Department of Critical Care Medicine
University of Pittsburgh

[name] [name].
Assistant Professor
Departments of Pathology & Critical Care Medicine
University of Pittsburgh
School of Medicine

Staff

[name], BS, BA
Project Manager
CRISMA Center
Department of Critical Care Medicine
University of Pittsburgh

[name], BS
Project Manager
CRISMA Center
Department of Critical Care Medicine
University of Pittsburgh

[name], BS
Project Coordinator
CRISMA Center
Department of Critical Care Medicine
University of Pittsburgh

[name], BA
Long-term Follow-up Manager
CRISMA Center
Department of Critical Care Medicine
University of Pittsburgh

Table of Contents

1	INTRODUCTION.....	8
A.	OBJECTIVE AND SPECIFIC AIMS.....	8
B.	BACKGROUND AND RATIONALE	8
C.	TRIAL DESIGN.....	9
2	METHODS	10
A.	PARTICIPANTS, INTERVENTIONS, AND OUTCOMES	10
i.	STUDY SETTING	10
ii.	ELIGIBILITY CRITERIA.....	10
a.	PARTICIPANT INCLUSION CRITERIA	10
b.	PARTICIPATION EXCLUSION CRITERIA	10
iii.	STUDY INTERVENTIONS AND PROCEDURES	11
v.	SAMPLE SIZE	14
vi.	RECRUITMENT AND CONSENT	14

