Lower respiratory tract infection (LRTI) is an ideal trial population. LRTI accounts for a large proportion of antibiotic prescription, and exemplifies the imprecise clinical phenotype of infection. Respiratory infection is the most common reason for ambulatory care visits, and accounts for >12 million annual ED visits.¹⁶ Determining which patients require antibiotics is difficult due to overlapping clinical presentations between LRTI subtypes and non-infectious conditions, and insensitivity of clinical exam and standard diagnostics for distinguishing bacterial from viral infection.

Important “proof of concept” trials using procalcitonin have been conducted. In 2004, a single center trial of 243 LRTI patients presenting to the ED of a Swiss academic hospital randomized patients to standard care or procalcitonin-guided care.¹⁷ In the procalcitonin arm, physicians were advised to withhold antibiotics if procalcitonin was low, and to administer antibiotics if procalcitonin was high. Procalcitonin-guided care halved antibiotic initiation with no apparent harm. The same research group achieved similar results in a 2007 single center trial of 208 COPD patients¹⁸ and a 2009 six center trial of 1359 LRTI patients powered for safety (ProHOSP).¹⁹ A recent single-center Shanghai study had similar findings.²⁰ However, key questions remain.

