Participants in the procalcitonin group will have one teaspoon of blood drawn for a procalcitonin level (\leq one hour after randomization goal) in the ED, and if hospitalized, 6-24 hours after the initial ED blood draw, and on Days 3, 5, and 7. Days 3, 5, and 7 blood draws for procalcitonin will only occur in hospitalized patients on antibiotics and/or at the treating clinician's discretion. For the purpose of this study, time zero is at randomization and Day 1 is defined as time of enrollment through 11:59PM of the same day.

In the ED, we will quickly (<1 hour goal) provide clinicians the procalcitonin result, accompanied by the procalcitonin antibiotic guideline (provided below). For participants who have not yet received antibiotics, we will ask the clinician to consider waiting for the procalcitonin result.

For patients admitted to hospital (or to an observation unit), we will inform the hospital clinician of the ED procalcitonin result, and that serial procalcitonin levels will be obtained, including a second one in 6 - 24 hours after the initial ED blood draw. During the hospital stay, study staff will inform clinicians when new serial procalcitonin results are available. The same procalcitonin guideline will be provided with both the initial and serial procalcitonin measurements - withhold or cease antibiotics if low, administer or continue if high.

Procalcitonin antibiotic guideline

Procalcitonin level (μ g/L)	Bacterial etiology	Recommendation
< 0.1	Very unlikely	Antibiotics strongly discouraged ¹
0.1 - 0.25	Unlikely	Antibiotics discouraged ¹
> 0.25 - 0.5	Likely	Antibiotics recommended ²
> 0.5	Very likely	Antibiotics strongly recommended ²

1. Initial antibiotics can be considered for critical illness, Legionella pneumophilia. Procalcitonin should be evaluated in context with all findings and the total clinical status; clinical judgment always necessary.

2. For outpatients, antibiotic duration based on level ($> 0.25-0.5 \mu$ g/L:3 days; $> 0.5-1.0 \mu$ g/L:5 days; $> 1.0 \mu$ g/L:7 days). Physician follow-up is recommended.

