Upon discharge (from ED or hospital) in the procalcitonin group, participants will receive a ProACT study information packet which includes a letter for their primary care clinician which provides an explanation of the study and the study guideline (Appendix 5), an instructional letter (Appendix 6), and a 30 day antibiotic use calendar (Appendix 7). This information packet will be provided to the participant as a tool to boost study awareness

and a reminder of the two subsequent phone visits described below. The 30 day antibiotic use calendar is an optional tool for the participant to aid in antibiotic use recall.

Study procedures specific to the usual care group:

After randomization, study staff will inform the treating clinician that the patient was assigned to the usual care group, and that procalcitonin will not be provided. At all times, all patient care is at the discretion of the treating clinician.

Upon discharge (from ED or hospital), usual care participants will receive a ProACT study information packet which includes an instructional letter (Appendix 6) and a 30 day antibiotic use calendar (Appendix 7). As stated above, this information packet will be provided to the participant as a tool to boost study awareness and a reminder of the two subsequent phone visits described below. The 30 day antibiotic use calendar is an optional tool for the participant to aid in antibiotic use recall.

Study procedures common to both groups:

1. All participants will have approximately four teaspoons of blood drawn in the ED after randomization. This blood sample will be sent to the CRISMA Molecular Core Laboratory at the University of Pittsburgh for research purposes related to procalcitonin, infection, and outcome.
2. All participants will have the following data collected during their ED visit:
 - Sociodemographic information
 - Comorbidities and current medications
 - Vital signs
 - Respiratory history
 - Test results and therapeutics relevant to current illness, including medications, significant lab values and imaging results
 - Antibiotics prescribed and received
 - Patient disposition upon ED discharge and ED final diagnosis
3. If admitted to hospital, both groups will have the following information collected from the medical record:
 - Antibiotics prescribed and received
 - Therapeutics and diagnostics (steroids, bronchodilators, radiologic test results)
 - Clinically obtained microbiology results
 - Disposition upon discharge

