For subjects that we have been unable to reach to complete 30 day interviews via phone call, we will send a letter informing the subject that we have attempted to reach them without success. This letter will include a toll-free number that subjects may call in order to schedule or complete their interview. Alternatively, we will also provide a paper version of the interview questions for those subjects that prefer to complete via paper. Subjects will be provided with a prepaid envelope to send back completed paper interviews. Subjects may receive an email message reminder for the interview that will include a link to a Qualtrics version of the survey that is identical to the paper version. Subjects who have agreed to receive text messages may also be prompted to complete the survey via text messaging.

In the event that the participant is hospitalized between ProACT study enrollment and Day 30 at a facility different from the enrolling site, a medical release will be requested for feasibility of long-term follow-up to ascertain clinical events related to the study (Appendix 10).

iv. OUTCOMES

Our **primary outcome** is total antibiotic exposure, defined as the total number of antibiotic-days by Day 30. We define an antibiotic-day as each day a participant receives any oral or intravenous antibiotics, excluding antibiotics given for non-infectious indications (e.g. neomycin for hepatic encephalopathy) and antivirals. Secondary outcomes include the rate of antibiotic initiation by the initial ED clinician.

Our **primary safety outcome** is a combined endpoint of adverse outcomes that could be attributable to withholding antibiotics in LRTI, that occur by study Day 30, as below. Our combined endpoint captures the components of the treatment failure endpoint used in a recent study of 80,000 COPD patients (death, mechanical ventilation, readmission).²² We assume no patient discharged from ED has met primary safety outcome endpoint at time of discharge (death, organ failure, empyema); post-discharge events are captured in follow-up. Secondary outcomes include vital status at Day 90 and 1 Year, as determined by National Death Index (NDI) query.

Measurable adverse events for primary safety outcome:

- i. death
- ii. septic shock (vasopressor use for > 1h)

- iii. mechanical ventilation (via endotracheal tube)
- iv. renal failure (KDIGO-3)
- v. lung abscess/empyema
- vi. development of pneumonia in non-pneumonia LRTI

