- vii. subsequent hospitalization (for both those discharged from ED and those admitted to hospital)

v. SAMPLE SIZE

We desire at least 80% power to conduct our primary hypothesis tests using a one-sided significance level of 0.05. As shown below, determination of sample size was dependent on the hypothesis test for the primary safety outcome, as this required a larger sample size than the tests for antibiotic exposure. Analyses were performed with SAS 9.1 (SAS Institute, Inc., Cary, NC). **Allocation of 757 subjects in each arm (total trial sample size of 1514) meets our goal of at least 80% power.**

Testing H1: Procalcitonin guideline implementation reduces the total number of antibiotic-days by Day 30.

For H1, ProHOSP reduced antibiotic exposure from 8.7 to 5.7 days (35% relative risk reduction). We chose a 20% relative reduction as an appropriate minimum threshold and to detect a lower effect size than ProHOSP.

We assumed control arm antibiotic exposure of 8 days, and calculated sample size based on a two-sided two-sample test at 0.05 significance. Under these assumptions, the sample size of 1514 required for H2 provides >99% power to detect a 20% relative reduction, and 80% power to detect a reduction of as low as one antibiotic-day (12% relative reduction). Power is preserved under a wide range of assumptions. Thus, we are exceptionally well-powered for H1.

Testing H2: Procalcitonin guideline implementation does not increase the proportion of subjects who experience a composite endpoint of adverse outcomes by Day 30.

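### Antibiotic initiation by the ED clinician is scored only on receipt in the ED, so a discharge prescription written without an ED dose counts as no initiation

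*SAP*

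**What the plan says.** The registration table at the front of the protocol names one key secondary outcome: "Rate of antibiotic initiation by the initial ED clinician". Protocol section 2.A.iv (Outcomes) repeats it: "Secondary outcomes include the rate of antibiotic initiation by the initial ED clinician". Neither place says how it is scored. The only rule is in the SAP, under Secondary outcomes: "antibiotic initiation by the initial ED clinician (reached if the patient received antibiotic during ED visit".

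Four other places bear on how that rule works:

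- Protocol 2.A.iii, procalcitonin-group procedures: "For participants who have not yet received antibiotics, we will ask the clinician to consider waiting for the procalcitonin result". The usual-care procedures contain no matching request.
- Protocol 2.A.iii, guideline footnote 2: "For outpatients, antibiotic duration based on level", followed by courses of 3, 5 or 7 days.
- Protocol 2.A.iii, procedures common to both groups: the ED data include "Antibiotics prescribed and received".
- SAP Table 1, ED row: antibiotics prescribed are recorded with their time, and disposition includes home.

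The SAP's secondary outcomes analysis will report a difference in proportions with a 95% confidence interval and treats all secondary outcomes as descriptive.

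**The concern.** The label credits an act to a particular clinician, while the rule records where and when the first dose was taken. The two part company when the ED clinician decides to treat but no dose is given before the patient leaves.

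The main case is the discharge prescription. Sending a patient home with a course is an ordinary ED treatment decision and one that the guideline addresses directly. Under the rule, such a patient looks the same as one sent home without antibiotics. If a low procalcitonin result leads the clinician not to write that prescription, the intervention has worked and this outcome cannot show it.

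The second case is an ED order whose first dose falls after ED exit. Because only procalcitonin-arm clinicians are asked to consider waiting, any slippage that this causes lowers the scored rate in that arm alone, with no change in the decision.

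What is at stake is interpretation. The background section reports of an earlier single-centre trial that "Procalcitonin-guided care halved antibiotic initiation with no apparent harm". Readers are likely to take this trial's figure as the matching effect on ED treatment decisions.

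**Working it through.** **Step 1. The rule applied to each route.** The protocol names prescribing and receiving as two things, so receipt does not naturally cover a prescription.

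| Route | ED clinician chose to treat | Scored as initiated |
|---|---|---|
| Dose given in the ED | yes | yes |
| No ED dose, prescription at ED discharge | yes | no |
| No ED dose, ED order first given on the ward | yes | no |
| No ED dose, hospital clinician starts treatment | no | no |
| No antibiotic | no | no |

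Rows two and three are misscored if the target is the ED clinician's decision. Row four is scored correctly.

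**Step 2. Figures in the plan.** Neither document gives an expected rate, effect size or power for this outcome, so there is nothing to reproduce.

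**Step 3. A hypothetical illustration.** Every rate below is assumed.

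- Patients per arm: 1,664 / 2 = 832 (SAP, Power and sample size).
- ED receipt in usual care 50%, half of it in patients then admitted.
- *u*, share of those not yet dosed when asked to wait: 0.50 to 0.75.
- *s*, share of those still treated whose first dose moves past ED exit: 0.05 to 0.20.
- *d*, share of all patients treated by discharge prescription only: 0.05 to 0.20.
- *r*, true relative reduction in treatment decisions, the same on every route: 0; 20%, borrowed from the antibiotic-day target ("We chose a 20% relative reduction as an appropriate minimum threshold"); 50%, from the earlier trial that halved initiation.

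Delay makes procalcitonin look better: delay = 0.50 × 0.50 × *u* × (1 − *r*) × *s*.

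Unseen averted prescriptions make it look worse: hidden = *d* × *r*.

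Net error = hidden − delay, where a positive value means the scored difference understates the effect. At *r* = 20%:

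- Delay: 0.25 × 0.50 × 0.80 × 0.05 = 0.5 points, up to 0.25 × 0.75 × 0.80 × 0.20 = 3.0 points.
- Hidden: 0.05 × 0.20 = 1.0 point, up to 0.20 × 0.20 = 4.0 points.
- Net: 1.0 − 3.0 = −2.0 points, up to 4.0 − 0.5 = +3.5 points. Of 832 patients that is about −17 to +29.

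| *r* | Delay (points) | Hidden (points) | Net error (points) |
|---|---|---|---|
| 0 | 0.6 to 3.75 | 0 | −3.75 to −0.6 |
| 20% | 0.5 to 3.0 | 1.0 to 4.0 | −2.0 to +3.5 |
| 50% | 0.3 to 1.9 | 2.5 to 10.0 | +0.6 to +9.7 |

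For scale, the 95% confidence interval half-width at rates near 50% is 1.96 × √(2 × 0.25 / 832) = 4.8 points.

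**Step 4. Where the sign turns.** With *k* = 0.25 × *u* × *s*, the two routes cancel at *r* = *k* / (*k* + *d*). That is 0.00625 / 0.20625 = 3% at one end and 0.0375 / 0.0875 = 43% at the other. The sign depends on inputs that the documents do not supply.

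**Step 5. Limits of the illustration.** With one common *r*, hidden prescriptions shrink only the absolute difference; they leave the relative reduction at *r*. The delay term omits first doses moved to home, so these ranges are not bounds. Other assumptions give other answers. If 60% in both arms are treated by ED decision, and 10% versus 20% of them take the first dose after the ED, the scored rates are 54% and 48%, a 6-point difference (95% CI 1.2 to 10.8) with no true effect.

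**The case against.** Initiation can fairly mean first receipt, and receipt is also the basis of the trial's antibiotic-day count. On that view the SAP gives an undefined label an objective, openly stated rule, and a prescribing measure is merely a different target with its own flaw: prescriptions may go unfilled. This stands to the extent that the rule is a legitimate measure of ED receipt and should be kept. It does not make that measure one of what the ED clinician decided.

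The ward-dose route is weak. Hospital clinicians also receive the result and the guideline, so a first ward dose may be their decision and is then rightly not credited to the ED. The request covers only undosed patients, asks clinicians only to consider waiting, aims for a result in under an hour, and reporting times are monitored (Protocol, Intervention adherence). This is accepted: slippage may be uncommon. The discharge-prescription route does not depend on it.

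The SAP also describes guideline congruence in terms of prescribing. Congruence is observable only in the procalcitonin arm, so it offers no comparison between arms.

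Finally, even the assumed errors need not change the message. At *r* = 20% the illustration gives a scored difference of 10.5 to 13 points against a true 11 to 14, and both would read as a clear reduction. That is a fair reason to rank the point low.

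**Conclusion.** The point holds as an optional improvement. On the text, a discharge prescription without an ED dose is scored as no initiation in both arms, and an averted one is invisible. An ED-ordered first dose given after ED exit is missed too, probably less often. This rests on a literal reading of the SAP's one scoring rule; the ED form itself is not in the documents.

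A reader might infer that the rule biases the result towards procalcitonin, because only that arm is asked to wait. The documents do not support this: they give no delay or discharge-prescription rates, and the second route pulls the other way. For the same reason the rule cannot be called conservative. The figures above are hypothetical and show only that the sign is open.

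Nor does the point weaken the trial's main antibiotic result. The primary outcome counts antibiotic-days in the ED, in hospital and after discharge (SAP, Primary outcomes), so treatment missed here is counted there. No hypothesis test, stopping rule or safety conclusion uses this outcome.

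**What to change.** Keep the current measure and label it 'antibiotic received in the ED'. Beside it, prespecify one supplementary descriptive row, computed alike in both arms: any antibiotic given in the ED, or ordered or prescribed by the ED clinician at that visit, including discharge prescriptions. Use the same difference in proportions and 95% confidence interval.

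The cost is about one SAP sentence and one table row. The ED data described in the protocol and in SAP Table 1 appear sufficient, but the sponsor should first confirm that the prescribed field covers discharge prescriptions. If it does not, the SAP's data collection section allows all data except the 30-day follow-up to be gathered retrospectively. The row should be fixed before unblinding, so that the definition cannot be chosen by its result.

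The downside is small: some prescriptions are never filled or taken, so the added row measures the decision to treat and not exposure. The label should say so.

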## **ADVERSE EVENTS**

We captured the major potential adverse events related to antibiotic withholding in our combined safety endpoint, and examine each adverse event using standard reporting methodology. We used the standard definitions of adverse events (AE) and serious adverse events (SAE) that met the definition of an Immediately Reportable Event (serious, unexpected AND related) within 48 hours of recognition; the coordinating center then notified the data and safety monitoring board (DSMB) and University of Pittsburgh IRB within 48 hours. All other AEs and SAEs were reviewed quarterly by the DSMB. When an AE/SAE occurred, it was the site PI's responsibility to review the pertinent records, and assess causality between the event and the study protocol using best clinical judgment. AEs were reviewed by the DSMB, which recommended follow-up or protocol modification, as deemed appropriate.

### III. DESIGN

#### DATA COLLECTION AND FOLLOW-UP

Site study coordinators collected data by direct observation, chart review, and subject or family member interview, and entered data into a Web-based form. This form was linked to a comprehensive server, provided built-in logic checks and queries, and had comprehensive training and instruction documentation to minimize site burden.

The stages of data collection and follow-up are randomization, baseline, ED, hospital follow-up, 30-day follow-up, and post-discharge survival. **Table 1** describes data that were collected at each stage. To further minimize site burden, all data except 30-day follow-up could be collected retrospectively.

#### TREATMENT ALLOCATION

We randomized subjects equally to either the procalcitonin guideline arm or usual care arm under a permuted block design, stratified by center, race, and age. The allocation list was computer generated and concealed within an automated centralized Web-based randomization system. This system ensures that treatment assignment is free from human influence. Only patients who met eligibility criteria and consented for participation were enrolled. The system assigned patients to a study arm only after enrollment. Coordinators entered participant information into the web-based data collection form then received a study ID number and treatment assignment from the randomization system.

